6.8.6. Vital Signs and Other Physical Findings

All vital signs data, height, and weight will be summarized and listed by visit/time points and cohort for patients on therapy.

6.8.7. Electrocardiograms

All ECG data will be analyzed for safety, and categorical analysis will be provided if appropriate. These ECG analyses may include the number and percentage of individuals with abnormal ECG findings or ECG parameters at scheduled time points as well as changes from baseline for ECG parameters.

6.9. Pharmacokinetic Analyses

Pharmacokinetic analyses will be conducted on patients who have received at least 1 dose of the study drug and have had samples collected. Pharmacokinetic parameter estimates for LY3022855, durvalumab, and tremelimumab will be calculated by standard noncompartmental methods of analysis. The primary parameters for analysis will be maximum concentration (C_{max}) and area under the concentration-time curve ($AUC_{0-tlast}$, $AUC_{0-\infty}$) of each of the study drugs. Other noncompartmental parameters, such as time of half-life ($t_{1/2}$), apparent clearance (CL/F), and apparent volume of distribution (V/F) for each study drug may be reported. Additional exploratory analyses will be performed if warranted by data and other validated PK software programs (for example, NONMEM) may be used if appropriate and approved by Global Pharmacokinetic management. The version of any software used for the analysis will be documented and the program will meet the Lilly requirements of software validation.

Pharmacokinetic parameter estimates will be evaluated to delineate the effects of dose proportionality, target-mediated drug disposition, and drug accumulation. Log-transformed C_{max}

and AUC estimates will be assessed to estimate ratios of geometric means and the corresponding 90% CIs. The potential effect of durvalumab-mediated programmed death-ligand 1 (PD-L1) inhibition and/or tremelimumab-mediated cytotoxic T-lymphocyte-associated protein 4 (CTLA-4) inhibition on the exposure of LY3022855 and the effect of LY3022855-mediated CSR-1 inhibition on the exposure of tremelimumab and/or durvalumab will be assessed using historical monotherapy exposure data for each of the 3 study drugs.

6.10. Pharmacodynamic Analyses

Pharmacodynamic analyses will be conducted on subjects who have received at least 1 dose of the study treatment(s) and have sufficient samples collected to allow the assessment of PD. Characterized profiles of available longitudinal biomarkers for estimable patients will be created and analyzed. Pattern recognition analysis may be applied for the PD biomarkers that indicate the evidence of drug engagement. Those include circulating levels of colony stimulating factor 1 (CSF-1), interleukin-34 (IL-34), cluster of differentiation (CD)14^{Dim}CD16^{Bright} monocytes, free membrane PD-L1, and monocyte markers.

6.11. Pharmacokinetic/Pharmacodynamic Analyses

Pharmacokinetic/pharmacodynamic analyses for LY3022855 may be conducted as deemed necessary by Global PK/PD management. These analyses may include, but are not limited to, establishing relationships (or lack of) between exposure and PD biomarkers that were explored or confirmed in PD analyses (refer to Protocol Section 10.6).

6.12. Immunogenicity Analyses

Immunogenicity data will be summarized, and correlation to drug level (each drug), activity, and safety will be assessed, as appropriate. The measures that will be analyzed include baseline presence and level of anti-drug antibody (ADA), treatment-emergent ADA, levels of neutralizing ADA, and incidence and levels of ADA related to infusion-related reactions.

6.13. Efficacy Analyses

Tumor response data will be tabulated by cohorts (according to Response Evaluation Criteria In Solid Tumors Version 1.1 [RECIST 1.1]). Particularly, the antitumor effect will be summarized by the overall response rate (defined by the total number of responses divided by the number of patients enrolled) and disease control rate (defined by the total number of stable disease + responses divided by the number of patients enrolled) by cohort and overall. Mean, median, range, and exact 95% CI will be provided. A patient is considered to have a tumor response if they achieve a confirmed CR or PR according to RECIST 1.1. Reported lesion measurement data, including sum of target lesions and change and/or percent change from baseline and nadir sum at each visit, will be listed for all patients on therapy. Investigator-determined response by cycle will be listed.

Time-to-event variables, such as progression-free survival (PFS), time to response (TTR), duration of response (DoR), and overall survival, will be listed and summarized. PFS time is defined as the time from the first dose of the study drug to objective progressive disease or death

due to any cause in the absence of disease progression. DoR is defined as the time from the first assessment of any tumor response to progressive disease or death due to any cause, occurring without observed disease progression. Patients not known to have progressed or died while on study will have their PFS and DoR time censored at the date of the last objective progression-free disease assessment. Patients for whom there is no record of progression, death, or postbaseline radiographic assessment will have their PFS time censored on the day of first dose of any study drug. TTR is defined as the time from the first dose of the study drug to the first assessment of confirmed response (CR or PR) by RECIST 1.1. DoR and TTR will be presented for each cohort for patients with a confirmed response (CR or PR). Overall survival is defined as the time from the first dose of study drug until death due to any cause. Patients with no reported death at analysis will be censored at their last reported date alive. For all time-to-event variables, the Kaplan-Meier method (Kaplan and Meier 1958) will be used to estimate the survival curves, medians, and survival rates at various time points, with 95% CI if applicable. For Part B, time-to-event variables will be summarized by cohort.

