8.1.2.2.3. During the 30-Day and 90-Day Follow-Up Visits

All AEs and SAEs, regardless of relatedness to study drug(s) or protocol procedures, occurring during the 30-Day and 90-Day Follow-Up visits (Visits 801 and 802) must be collected (captured on the eCRF; in the case of an SAE, also on the SAE form) and reported to Lilly or its designee. The 30-Day Follow-Up visit (Visit 801) begins the day after the patient and investigator agree that the patient will no longer continue to receive study treatment. The duration of this follow-up visit is 30 days (± 7 days). At the end of the 30-Day Follow-Up visit, the patient will be required to have specific safety assessments ([Attachment 1](#)). If it is deemed to be in the best interest of the patient to start a new anticancer treatment prior to the scheduled end of the follow-up visit, the duration of the visit may be shortened. In this case, the follow-up assessments should be completed prior to the initiation of the new therapy.

The 90-Day Follow-Up visit (Visit 802, only for durvalumab and tremelimumab safety) occurs 90 days (± 7 days) after the patient and investigator agree that the patient will no longer continue to receive study treatment. Refer to [Attachment 1](#) for specific safety assessments to be conducted during the 90-Day Follow-Up visit.

Following the safety assessments that mark the end of the follow-up visits (30-Day Follow-Up visit [Visit 801], for LY3022855, durvalumab, and tremelimumab safety, and 90-Day Follow-Up visit [Visit 802], only for durvalumab and tremelimumab safety), the patient will be discontinued from the study, unless there is an ongoing AE or SAE that is possibly related to study drug. In this instance, the patient should continue to be followed by extending the duration of the follow-up visit until the event is resolved, the event is no longer considered to be drug related, the event becomes stable or returns to baseline, a new treatment is initiated for the patient, or the patient dies or is lost to follow-up.

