10.8. Efficacy

Tumor response data, according to RECIST 1.1 (Eisenhauer et al. 2009), will be tabulated by cohorts. Particularly, the antitumor effect will be summarized by best overall response, including the overall response rate (ORR) and disease control rate (DCR; CR+PR+SD). A patient is considered to have a tumor response if they achieve a confirmed CR or PR. The ORR is estimated by the proportion of enrolled patients who have a best overall response of confirmed CR or PR. The DCR is estimated by the proportion of enrolled patients who have a best overall response of confirmed CR, confirmed PR, or stable disease. A 95% exact CI will be constructed to determine the level of precision of the ORR and DCR. Time-to-event variables such as progression-free survival (PFS), time to response, duration of response, and overall survival (OS) will be tabulated if appropriate. The Kaplan-Meier method (Kaplan and Meier 1958) will be used to estimate the survival curves, medians, and survival rates at specified time points, if applicable.

Upon completion of each Part B cohort, an analysis of safety, PK, pharmacodynamics, biomarkers, and efficacy may occur, once all patients have completed 4 cycles of study therapy or discontinued from the study.

Any cohort-specific analyses may be combined if they are expected to occur within approximately a month, and the analyses may also be combined with the ongoing trial-level safety review or annual safety review for annual safety update reporting.

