CTCAE v4.0 grading	X	X	X	X	X		Throughout study as needed. Refer to Section 8.1.1 for reporting guidelines.
Concomitant medications	X	X	X	X	X		Throughout study as needed.
LY3022855 administration	Refer to Table JSCC.1 for dose frequency during Part A.						For LY3022855 and durvalumab: Part A doses: Refer to Table JSCC.1 .
Durvalumab administration	X		X				Part B doses and dose frequencies to be determined; refer to Section 7.2.2.2 for information.
Pharmacokinetics							
LY3022855					X		The date and the time of all samples must be clearly and accurately recorded.
Durvalumab					X		
Pharmacodynamics and tailoring							
Serum					X		Serum storage for correlative studies.
Plasma					X		Plasma storage for correlative studies.
Whole blood					X		Exploratory research.
Flow cytometry							
Immunophenotyping #1							CD14, CD16.
Immunophenotyping #2							TBNK & T cell subset/activation panels.
Immunophenotyping #3							MDSC panel.
Isoenzymes (central)							Refer to Attachment 2 . Obtain at additional time points, as clinically indicated.
LVEF evaluation							Echocardiogram or MUGA scan. Obtain at additional time points, as clinically indicated.
Radiographic tumor assessment (CT/MRI)				X	X		Perform every 8 wk (± 7 d), starting on Cycle 2, Day 22, then every 12 wk (± 7 d) for patients who achieve disease control after 12 mo of study treatment and after Week 48 for patients who discontinue durvalumab due to toxicity or symptomatic deterioration. For patients who continue on durvalumab post-confirmed progression at the investigator's discretion (after consultation with the sponsor), tumor assessments should be performed until durvalumab is stopped.
Tumor measurement (palpable or visible)				X	X		
Tumor biopsy							For Part A (all cohorts) and Part B (ovarian cancer cohort only): An on-treatment tumor core needle or excisional biopsy to be performed 6-8 wk after starting study treatment.

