Relative day within a 28-day cycle:	1	8	15	22	1	8	15	22	X		*90-Day Follow-Up visit is only for tremelimumab safety.
Serum									X		Serum storage for correlative studies.
Plasma									X		Plasma storage for correlative studies.
Whole blood									X		Exploratory research.
Flow cytometry											
Immunophenotyping #1											CD14, CD16.
Immunophenotyping #2											TBNK & T cell subset / activation panels.
Immunophenotyping #3											MDSC panel.
Isoenzymes (central)											Refer to Attachment 2 . Obtain at additional time points, as clinically indicated.
LVEF evaluation											Echocardiogram or MUGA scan. Obtain at additional time points, as clinically indicated.
Radiographic tumor assessment (CT/MRI)				X				X		X	Perform every 8 wk (± 7 d), starting on Cycle 2, Day 22, then every 12 wk (± 7 d) for patients who achieve disease control after 12 mo of study treatment and after Week 48 for patients who discontinue tremelimumab due to toxicity or symptomatic deterioration. For patients who continue on tremelimumab post-confirmed progression at the investigator's discretion (after consultation with the sponsor), tumor assessments should be performed until tremelimumab is stopped.
Tumor measurement (palpable or visible)				X				X		X	
Tumor biopsy											For Part A (all cohorts) and Part B (ovarian cancer cohort only): An on-treatment tumor core needle or excisional biopsy to be performed 6-8 wk after starting study treatment.

Abbreviations: AE = adverse event; BP = blood pressure; CnDn = Cycle n, Day n (for example, C1D1 = Cycle 1, Day 1); CK = creatine kinase; CT = computed tomography (scan); CTCAE = Common Terminology Criteria for Adverse Events; ECG = electrocardiogram; ECOG = Eastern Cooperative Oncology Group; EOI = end of infusion; hCG = human chorionic gonadotropin; IRR = infusion-related reaction; LVEF = left ventricular ejection fraction; LY = LY3022855; MDSC = myeloid-derived suppressor cell; MRI = magnetic resonance imaging; MUGA = multigated acquisition (scan); NCI = National Cancer Institute; PK = pharmacokinetic(s); PR = pulse rate; RR = respiration rate; T3 = triiodothyronine; T4 = thyroxine; TSH = thyroid-stimulating hormone; v4.0 = Version 4.0 of NCI-CTCAE.

^a No follow-up procedures will be performed for patients who withdraw informed consent unless he or she has explicitly provided permission and consent.

Continued Access Schedule for Combination Therapy: LY3022855 plus Tremelimumab

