6.4. Patient Disposition

A detailed description of patient disposition will be provided. It will include summaries of the number and percentage of patients entered into the study, enrolled in the study, and completing the study (with data indicating completion of study primary and secondary objectives in electronic case report form page of the End of Study), and reasons for discontinuation from study treatment, as well as discontinuation from the study. All patients entered in the study will be included in the summary. Reason for discontinuation from both study treatment and the study will be listed by the pre-determined categories. If the reason for discontinuation is AE or death, the associated AE or cause of death will be reported.

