6.8.4. Deaths, Other Serious Adverse Events, and Other Notable Adverse Events

A summary of deaths will be presented by cohort and overall. Reasons for death will be summarized separately for deaths on therapy, within 30 days of discontinuation of study therapy (counting from the date the decision to discontinue treatment is made) and after 30 days of discontinuation of study therapy. Other listings include:

- Listing of Deaths
- Listing of Serious Adverse Events
- Listing of Subjects who Discontinued due to Adverse Events of Death

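### SAP 6.13 commits to Kaplan-Meier overall-survival medians although no survival contact is scheduled after Visit 802, so the censoring is informative

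*SAP*

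**What the plan says.** SAP 6.13 lists OS among the time-to-event variables to be listed and summarized. It runs from first dose to death from any cause, and "Patients with no reported death at analysis will be censored at their last reported date alive". For all time-to-event variables the Kaplan-Meier method "will be used to estimate the survival curves, medians, and survival rates at various time points, with 95% CI if applicable". The closing condition most naturally belongs to the confidence interval, not to the medians and rates.

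Protocol 10.8 is softer. Time-to-event variables such as PFS, response times "and overall survival (OS) will be tabulated if appropriate", and its Kaplan-Meier sentence is also conditional.

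Follow-up is set in Protocol 8.1.2.2.3. Visit 802 falls 90 days (±7) after patient and investigator agree to stop study treatment. After the follow-up visits "the patient will be discontinued from the study, unless there is an ongoing AE or SAE that is possibly related to study drug".

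Attachment 1 has two post-treatment columns, Visits 801 and 802, and no survival-status row. Continued access (Visits 901 and 902) repeats the same 30-day and 90-day pattern.

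**The concern.** A Kaplan-Meier estimate needs censoring that is unrelated to the risk of death. Here the usual reason for losing contact is that the patient stopped treatment, mostly because the disease progressed, and then passed Visit 802. Patients with progressed disease are at higher risk, and they are removed from the risk set about three months later. Patients still on treatment stay in it. The estimate then reflects mainly the lower-risk group.

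Later deaths have no scheduled source:

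- Table JSCC.4 limits reporting for patients no longer on study to SAEs related to study drug or procedures that the investigator learns of.
- Protocol 8.1.2.1 keeps deaths from progression out of SAE reporting unless possibly drug related.

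Antitumor activity is a secondary objective and every analysis is descriptive. A published OS median would therefore be read as the result itself, with no test or decision rule standing between it and the reader.

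**Working it through.** **1. How far scheduled contact reaches.** Study day = (cycle − 1) × 28 + day. The first scan, Cycle 2 Day 22, is day 28 + 22 = 50. The second, eight weeks later, is day 106. If treatment stops on the scan day:

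- stop at day 50: last scheduled contact 50 + 90 = day 140 (133 to 147), or 140/30.4375 = 4.6 months;
- stop at day 106: last scheduled contact 106 + 90 = day 196 (189 to 203), or 6.4 months.

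With an assumed exponential OS median of 12 months, deaths by then are 1 − 0.5^(4.60/12) = 23% and 1 − 0.5^(6.44/12) = 31%.

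**2. Share of deaths observed.** The documents give no survival assumptions, so these inputs are assumed: exponential PFS with median 2 or 4 months; exponential post-progression survival with median m = 4, 6, 9 or 12 months; a share q = 0, 0.1 or 0.2 of PFS events being deaths; treatment stopped at progression; censoring 3 months later (Visit 802); no later death known.

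Observed share = q + (1 − q) × (1 − 0.5^(3/m)).

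- Lowest: q = 0, m = 12 gives 1 − 0.5^0.25 = 0.159.
- Highest: q = 0.2, m = 4 gives 0.2 + 0.8 × 0.405 = 0.524.

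So about 16% to 52% of deaths are observed.

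**3. Effect on the Kaplan-Meier median.** Simulation with 1,000,000 patients per setting for the median and 4,000 cohorts of 20 (the Part B cohort size) for the chance that it is not reached. Times are in months.

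| q | PFS median | m | Deaths observed | True median | KM median | Error | Not reached, n = 20 |
|---|---|---|---|---|---|---|---|
| 0 | 2 | 4 | 41% | 7.08 | 8.13 | +15% | 20% |
| 0 | 2 | 12 | 16% | 15.11 | 20.71 | +37% | 76% |
| 0 | 4 | 12 | 16% | 18.31 | 33.12 | +81% | 70% |
| 0.1 | 2 | 4 | 46% | 6.50 | 7.09 | +9% | 12% |
| 0.1 | 4 | 9 | 29% | 13.89 | 18.88 | +36% | 40% |
| 0.2 | 4 | 6 | 43% | 10.18 | 12.11 | +19% | 12% |
| 0.2 | 2 | 12 | 33% | 11.27 | 10.89 | −3% | 45% |
| 0.2 | 4 | 4 | 52% | 8.49 | 9.91 | +17% | 4% |

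Over all 24 settings only one error is negative. Repeat runs put the extremes at −4% to −3% and +77% to +81%; the upper end varies because few patients are still at risk that late. The chance of no median is about 3% to 77%.

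**4. If some late deaths are learned of.** Suppose data cuts fall uniformly over 12 to 24 months and survivors stay censored at Visit 802. If 25% of deaths after Visit 802 are learned of, the error runs from −18% to +15%; if 50%, from −25% to +7%. If all are, it runs from −30% to −1%. Each such death counts as an event while comparable survivors have already left the risk set, so the median is pulled down.

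**The case against.** The strongest reply is that the protocol already covers this. Section 10.8 makes OS conditional, and the protocol (February 2018) is later than the SAP (Version 1, April 2016). OS is one example in a descriptive secondary analysis, and no dose or cohort decision uses it. All of that stands and keeps the point minor. It does not remove it: the SAP is the document an analyst would execute, and its OS sentence is unconditional.

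A second reply is that the size rests on assumptions. That is also true. Treatment may continue past progression (Protocol 6.3.2), follow-up may be extended for a related AE, and the eCRF is not available here, so the number of late deaths captured is unknown. SAP 6.4 does record death as a reason for discontinuation ("If the reason for discontinuation is AE or death, the associated AE or cause of death will be reported"), but that is not follow-up after a patient has left the study.

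A reader might also infer more than the documents support:

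- **That the bias could equally go either way.** The shortening in step 4 needs a sizeable share of late deaths to be learned of. The reporting rules point to few, so too long is the more likely direction.
- **That the Attachment 1 scan comments contradict leaving at Visit 802.** They describe 12-weekly scans "after Week 48 for patients who discontinue durvalumab due to toxicity or symptomatic deterioration", and likewise "after Week 48 for patients who discontinue tremelimumab due to toxicity or symptomatic deterioration". Those patients have stopped one drug, whereas 8.1.2.2.3 concerns stopping study treatment. Protocol 7.2.4.1 allows one drug to be stopped alone, so a patient still on LY3022855 could have these scans before reaching Visit 802. No conflict is established.
- **That the death summary in SAP 6.8.4 is defective.** Its open category, "and after 30 days of discontinuation of study therapy", is a valid safety grouping; a further cut at Visit 802 is optional.
- **That the eight-week confirmation minimum, equal to the scan interval, is an error of the same kind.** An in-window day at 56 days or later always exists. If sites follow Protocol 8.3, the loss of confirmed responses against next-scan confirmation is about 0.7% to 2.7% for assumed median response durations of 52 to 13 weeks.

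**Conclusion.** Wrong as written, minor severity. SAP 6.13 promises OS medians and rates that the scheduled follow-up cannot support without informative censoring. That conclusion needs no simulation; it follows from the discontinuation rule, the visit schedule and the limits on off-study reporting.

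The size does depend on the exponential model, on stopping treatment at progression, and on no late death being known. On those terms the OS median is off by about −4% to +80%, mostly too long, and often not reached in a cohort of 20. Neither dose selection nor any error rate is affected.

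**What to change.** In SAP 6.13, take OS out of the unconditional Kaplan-Meier sentence. State that OS medians and rates will be produced only if vital status is actually collected after Visit 802, in line with Protocol 10.8. Otherwise report deaths as counts and a listing through Visit 802, and list later-learned deaths separately.

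The cost is a few sentences, with no new visit and no protocol change. The SAP needs updating in any case: section 5.1 still plans 178 patients (78 + 100) against 118 (78 + 40) in Protocol 10.1. The downside is that the report may contain no OS median.

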6.14. Tailoring Biomarker Analyses/Companion Diagnostic Analyses

If applicable, efficacy measures may be summarized descriptively within subgroups of patients. Exploratory analyses may be applied to evaluate the association between baseline biomarkers and clinical outcome. If applicable, a subset of potential predictive biomarkers associating with interpretable clinical benefit may be further examined with biological evidence. Biomarker analyses related to the exploratory objectives of this study will be described in a separate SAP.

